### Objective 1 specific methods:

**Evaluate the efficacy of HITSystem 2.1 to increase the proportion of womens who receive complete PMTCT services through 6 m postpartum, per Kenyan guidelines.**

**Objective 1 outcomes.** The primary outcome for Objective 1 is the proportion receiving "complete PMTCT," an aggregate measure incorporating the documented receipt of all

designated services across the 3 PMTCT phases: maternal ART initiation, antenatal appointment attendance, facility delivery, EID linkage by 7 weeks of age, maternal VL testing and clinical action per national

Table 6. Aim 1 primary outcome: Services required for "complete PMTCT"

| Antenatal  | Delivery                | Postpartum (through 6m)   |
|--|-------------------------|---|
| 

• ART initiation

• On-time appointment attendance

• VL testing per guidelines

• Clinical action upon detectable VL

 | Hospital-based delivery | 

• EID linkage by 7 weeks

• VL testing per guidelines

• Clinical action upon detectable VL

 |

guidelines through 6 months postpartum (Table 6). Participants who receive all indicated services per guidelines will be coded as 1 or 'yes'. Participants missing  $\geq 1$  service will be coded as 0 or incomplete PMTCT services.

**Secondary outcomes** associated with Objective 1 will include gestational week at PMTCT enrollment, duration of PMTCT retention (weeks), and ART adherence (proportion >95%, proportion with missing/late prescription refill). Proportions will be calculated to describe each component of "complete PMTCT" separately (appointment attendance, VL monitoring, hospital delivery, EID linkage). Patient and facility-level factors will be assessed for their moderating impact on complete PMTCT. Provider characteristics will be aggregated and treated as facility-level variables. To assess pathways through which the HITSystem 2.1 works, we will measure provider and patient information and motivation as potential mediators

both pre- and post-intervention, and across study arms. Preterm births and infant weight at birth will be documented. We also will measure the proportion and timing/age of any HIV transmissions to infants, and maternal and/or infant deaths.

**Statistical analyses for objective 1 (complete retention).** Data from women who have a documented reason for incomplete care at the study hospital (e.g. transfer facility, pregnancy loss, maternal death) will not be included in analyses. To demonstrate the efficacy of HITSytem 2.1 versus SOC, we will test for differences between arms by modeling complete PMTCT as a function of study arm and selected covariates (e.g., age, partner support, depression) using logistic mixed models with a random site intercept (to adjust for clustering). In post hoc analyses we will explore patient and facility-level characteristics as potential moderators of the effect of HITSytem 2.1, and examine changes in key individual level factors (disclosure status, partner status, depression, partner support) at the midpoint (delivery) and again at the end (6m postpartum). To assess mediating factors, we will compute average levels of provider knowledge and motivation for each site at baseline and end of study. These knowledge and motivation scores, as well as patient knowledge and motivation levels, will be compared pre-post intervention and between study arms to assess change within and between sites. In addition, provider and patient knowledge and motivation will be examined as predictors of PMTCT completion using logistic regression.

[figure not shown]

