### 5.0 Designs and methodology

**Study Design:** This will be a hybrid 1 study design (mixed methods), where we are testing effects of a clinical intervention on relevant outcomes while observing and gathering information on implementation. We propose a matched cluster randomized controlled trial (2 arms, 6 clusters/arm, n=75 participants per cluster), using mixed methods. We will enroll PMTCT clients at Kenyan health facilities offering either HITSystem 2.1 intervention or standard of care (SOC) services to evaluate the efficacy, implementation, and cost-effectiveness of HITSystem 2.1 to increase complete PMTCT retention and viral suppression. Participants will be enrolled in PMTCT and followed through 6 months postpartum, with focused data collection at enrollment, delivery, and 6 months postpartum, Figure 1.

**(a) Study sites:** Study sites will be located in Siaya, Mombasa, and Kilifi Counties. These counties were selected due to their (1) elevated MTCT rates and (2) lower density of interventions targeting MTCT that could confound the results of this evaluation. To be eligible for selection and matching in the study, health facilities must (1) provide PMTCT, EID, and ART services and (2) not be involved in any ongoing PMTCT or EID interventions or research studies.

We will collaborate closely with the national PMTCT technical working group to facilitate strategic site selection to maximize the similarity of facilities matched on geographic region, patient volume, and HIV prevalence. Finalized matches are outlined in Table 2.

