**Table 2: Proposed matched sites.**

| Intervention Site | Control Site   | Region |
|-------------------|----------------|--------|
| Mariakani         | Vipingo        | Coast  |
| Mtwapa            | Likoni         | Coast  |
| Bondo Referral    | Siaya Referral | Siaya  |
| Malanga           | Yala           | Siaya  |
| Ukwala            | Sigomere       | Siaya  |
| Ambira            | Akala          | Siaya  |

**Randomization:** All eligible facilities will be yoked in matched pairs. The study statistician will then randomly allocate one site in each pair to the intervention. Use a random number generator program to randomly allocate one site in each pair to the intervention. The study statistician will be blind to the process of choosing the sites. Similarly, all other research staff will be blind to the randomization process.

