### **(c) Sampling**

All HIV-positive pregnant women who present for care at study hospitals will be eligible for enrollment in the study. All eligible study candidates will be informed of the purpose of the research, including potential benefits and risks, prior to a request for written informed consent (Appendices 2A and 2B, see detailed informed consent section below). Women opting out of the study at intervention sites will have the option to either (1) access standard PMTCT services without enrollment in HITSystem 2.1, or (2) access HITSystem 2.1-supported PMTCT without their data being included in study analyses. Women opting out of the study at control sites will receive standard PMTCT services with their data being excluded from study analyses. Mentor mothers will document study enrollment and enrollment refusal at all sites.

Providers participating in interviews will be purposively sampled to represent a range of clinical departments and roles involved in the provision of PMTCT services.

**Sample size determination for Objective 1:** We estimated current levels of retention in complete, guideline-adherent PMTCT services based on findings from our R34 grant. Findings from our retrospective review at 4 Kenyan health facilities indicate only 50/424 (11.8%) of women enrolled in PMTCT received guideline adherent viral load testing. Based on average percentage point increases in complete retention achieved in previous studies (33% HITSytem 2.0 pilot [R34], 25% HITSytem 1.0 [R01]), we conservatively anticipate HITSytem 2.1 supported VL testing will exceed that of SOC by at least 20 percentage points (Table 3). We assume that the small subset of participants with guideline-adherent VL testing will be included among the larger population of those receiving complete PMTCT retention. To account for increased familiarity with guidelines over time and continually improving SOC, we assessed statistical power for contingencies with SOC guideline adherence as high as 18% using R package *clusterPower*. Assuming ICC=.05, the planned sample size of six 75-person clusters per arm provides 85% power to detect differences even smaller than the expected 20-percentage point difference across a range of possible SOC completion rates (Table 4). Using HITSytem 2.0 pilot data, we predict 28% attrition; thus, we need to enroll **n=96 women per cluster** (75 + 21).

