**Sample size considerations for Objective 2.** We draw upon limited pilot data, given the dearth of published data describing VL among women in pregnancy and in the postpartum periods, or estimates of VL of women who have disengaged from care in either period. Among PMTCT clients who received at least one VL test result, 31.3% of women in the control site had a detectable VL. Albeit small numbers, in the R34 intervention site which received intensified PMTCT retention support, but no prompts for VL testing or clinical action, 2/22 (9.1%) women had a detectable VL >1,000. These proportions reflect women engaged in clinical care during the study period. We estimate that women LTFU will have at least a 50% increased risk of a detectable VL given likely treatment interruption. In the control site, 24% of women were LTFU by the time of delivery, thus when averaging estimates for all women (retained and LTFU) we estimate 35% of women enrolled in SOC PMTCT will have a detectable VL compared to 10.2% (rounded up to 11%) in the HITSytem 2.1 sites (Table 5). With the strengthened VL component of HITSytem 2.1, we believe this estimate of 11% or less is realistic for the intervention arm. Using the R package *clusterPower*, we estimated power to detect a difference in proportions of detectable VL of .35 and .11. In an effort to demonstrate superiority of HITSytem 2.1 before accrual is complete, we will carry out an interim analysis after accruing 67% of the planned sample size in each arm. Splitting  $\alpha$  evenly between this interim analysis and the final analysis to preserve the overall  $\alpha$ -level at .05, power to detect the hypothesized .35 vs. .11 difference in the interim analysis at  $\alpha=.025$  is 95%. For a smaller difference of .30 vs. .11, power is 83% for the interim. Including the final analysis provides additional power. With the same estimates for attrition as detailed in Objective 1, the same number of participants are required for Objectives 1 & 2 (n= 75/cluster). However, a national stockout of viral load and infant HIV testing reagents caused a significant number of our sample to miss viral load and EID testing required for our aim 2 analyses. We have developed procedures to support postpartum VL testing and infant EID testing for the study (see below), however, prior to establishing these protocols, a total of 198 women and 320 infants missed routine testing due to this shortage. Two sites have already stopped enrolling, since they have met their required sample size of n=96 per site. We seek to add a total of n=30 participants to the ten sites that are still enrolling – for a total of n=300 participants across the study - to offset the statistical power lost due to missed testing from the national shortage. This would bring our total enrolled sample to n=1,452. We would enroll this sample for both aims 1 and 2, since both aims use the same patient population.

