test efficiency (turn-around time from sample to result, and turn-around time from result to patient notification), VL test utility (proportion of detectable VL results with clinical action per guidelines, such as: intensified adherence counseling and/or ARV regimen change), and repeated VL testing among those with detectable VL. We will document outcomes for pregnant and breastfeeding women who are LTFU to better enumerate outcomes for this population.

**Statistical analyses for Objective 2.** We will test for differences on binary outcomes between arms using logistic mixed models with adjustment for clustering and select covariates. After transformation (e.g., log) of turn-around time values if needed, differences in time will be assessed using appropriate generalized or linear mixed models. Post hoc analyses will assess person-level characteristics as moderators of the HITSystem 2.1 effect to assess whether the HITSystem 2.1 is more effective for specific subgroups. Any differences will guide future adaptations to improve efficacy among specific populations. The same methods described for mediation analysis of information and motivation will be applied in Objective 2.

Objective 3 specific methods:

**Evaluate the reach, effectiveness, adoption, implementation fidelity and maintenance (REAIM model) of HITSystem 2.1 using system data and surveys with providers and patients.**

We will evaluate the implementation of HITSystem 2.1 components to guide programmatic implementation and increase sustainable use in government health facilities. The RE-AIM framework is well suited to evaluate the implementation of system-level interventions, and outlines the public health impact as the intersection between: Reach, Effectiveness, Adoption, Implementation, and Maintenance, Table 6.

**Reach:** We will assess the proportion of eligible participants enrolled in HITSystem 2.1 at intervention sites by comparing HITSystem 2.1 enrollment with paper-based PMTCT registers. Reasons for non-participation will be documented for all eligible participants not included in the study. Among participants, data collected through the patient enrollment surveys will be used to describe characteristics of the sample and compared with national estimates to assess representativeness to national population of HIV+ pregnant women.

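### Twelve pair-matched sites are to be analysed with no pair term and no small-sample method, and the stated power matches a large-sample unpaired test

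*Combined protocol and SAP*

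**What the plan says.** Section 5.0 (Study Design) describes the trial thus: "We propose a matched cluster randomized controlled trial (2 arms, 6 clusters/arm, n=75 participants per cluster), using mixed methods". The Randomization paragraph below Table 2 says "All eligible facilities will be yoked in matched pairs" and "The study statistician will then randomly allocate one site in each pair to the intervention". Table 2 lists six pairs.

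The Objective 1 analysis models complete PMTCT on study arm and chosen covariates "using logistic mixed models with a random site intercept (to adjust for clustering". The Objective 2 analysis uses "logistic mixed models with adjustment for clustering and select covariates". Neither paragraph mentions the pairs, the test statistic, degrees of freedom or a correction for few clusters.

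On power, section 5.0(c) states: "Assuming ICC=.05, the planned sample size of six 75-person clusters per arm provides 85% power". It adds that this holds for differences below 20 percentage points and for standard-of-care (SOC) rates up to 18%; Table 4 itself stops at 14%. For Objective 2 there is an interim test at two-thirds accrual and alpha .025, with 95% power for .35 vs .11. The plan then says "For a smaller difference of .30 vs. .11, power is 83% for the interim". The power method is described as simulation with generalized linear mixed models; pairing is not mentioned.

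**The concern.** The treatment effect rests on 12 sites. Unpaired, about 10 degrees of freedom are available to judge it; fully paired, there are 5. Large-sample tests from a mixed model treat the between-site variance as well estimated, which it is not with six sites per arm, and they tend to reject too often. Leaving out pairs that do share variance works the other way: the standard error is too large and the test becomes conservative. The plan does not say which test will be read off the model, so the error rate of both primary comparisons, and of the interim superiority test, is left open. If the sample size was justified with a test more liberal than the one finally used, the stated power is also too high.

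**Working it through.** **Inputs from the plan.** Six sites per arm; 75 analysed per site; ICC .05; Table 4 rates; interim at 67% of the sample (0.67 × 75 ≈ 50 per site) with alpha .025. Assumed: two-sided tests, equal site sizes, no covariates.

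**Step 1: reproduce the stated power.** Effective n per arm = 6m / [1 + (m − 1) × .05].

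- m = 75: 450 / 4.70 = 95.7
- m = 50: 300 / 3.45 = 87.0

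δ = |p1 − p2| / √[(p1q1 + p2q2) / n_eff]; power = Φ(δ − z).

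- .12 vs .30: SE = √[(.1056 + .2100) / 95.7] = .0574; δ = 3.135; Φ(3.135 − 1.960) = 88.0%
- .35 vs .11, interim: SE = √[(.2275 + .0979) / 87.0] = .0612; δ = 3.923; Φ(3.923 − 2.241) = 95.4%
- .30 vs .11, interim: SE = .0595; δ = 3.193; Φ(3.193 − 2.241) = 82.9%

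The formula also returns every minimum difference in Table 4 at a resolution of one point: the stated .16, .17, .18 and .18 give 87.2%, 87.4%, 88.0% and 85.8%, and one point less gives 83.4%, 83.8%, 84.6% and 82.0%.

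**Step 2: same δ, noncentral t.** Critical values are 2.228 (10 df) and 2.571 (5 df) at .05, and 2.634 and 3.163 at .025. The 5-df column assumes no matching gain.

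| Comparison | Stated | Normal | 10 df | 5 df, paired |
|---|---|---|---|---|
| .08 vs .24 | 85% | 87% | 80% | 70% |
| .10 vs .27 | 85% | 87% | 80% | 70% |
| .12 vs .30 | 85% | 88% | 81% | 71% |
| .14 vs .32 | 85% | 86% | 78% | 68% |
| .12 vs .32 (planning case) | not given | 93% | 87% | 78% |
| .18 vs .38 (SOC contingency) | 85% claimed | 89% | 81% | 72% |
| .35 vs .11, interim | 95% | 95% | 88% | 75% |
| .30 vs .11, interim | 83% | 83% | 71% | 56% |

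**Step 3: type I error with uninformative pairs.** Simulated trials (4,000 per scenario, 12 sites, ICC .05 on the proportion scale) were fitted with a maximum-likelihood random-intercept logistic model. At nominal 5%, with 75 per site and rates of .12, .18 and .35:

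- Wald z: 9.8–10.6%
- likelihood-ratio test: 7.3–7.8%
- Wald with 10 df: 6.1–7.3%
- site-level t-test, 10 df: 4.2–4.9%
- paired site-level t-test, 5 df: 4.3–4.7%

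At the interim (nominal 2.5%, 50 per site), Wald z gives 6.1–6.3% and the likelihood-ratio test 4.0–4.1%.

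**Step 4: let the pairs share between-site variance.** The share is an assumption. Error is at nominal 5% with an event rate of .12; interim power is at .025.

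| Share | Wald z error | Paired t error | Paired t power, .12 vs .30 | .35 vs .11, interim | .30 vs .11, interim |
|---|---|---|---|---|---|
| 0% | 10.6% | 4.3% | 72% | 75% | 59% |
| 25% | 8.1% | 4.6% | 81% | 81% | 66% |
| 50% | 5.0% | 3.8% | 89% | 91% | 74% |
| 75% | 2.6% | 3.9% | 97% | 97% | 88% |

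The 0% row is simulated, so it differs slightly from Step 2.

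**The case against.** The plan names a model class, not a test. That a power figure matches normal critical values does not commit the analysis to a Wald z test; the same model can be reported with a likelihood-ratio test or corrected degrees of freedom. This stands. A reader might infer that both primary tests run at double their nominal level, but that needs Wald z and matching that explains nothing. Sites were matched on region, patient volume and HIV prevalence, so no gain at all is not the natural default.

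A reader might also infer that ignoring the pairs causes the inflation. It does not: Step 4 shows that omitting informative pairs lowers the Wald z error and offsets the few-clusters problem.

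Nor does the claim that the design "provides 85% power to detect differences even smaller than the expected 20-percentage point difference" fail in general. With 10 df, a 20-point difference has 92%, 90%, 87% and 85% power at SOC rates of 8%, 10%, 12% and 14%. It falls short at the 18% contingency, with 81%.

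The 95% and 83% are interim figures, and the plan says the final analysis adds power. Covariates may also absorb some between-site variance. Finally, if ICC .05 were meant on the latent logit scale, site variance would be smaller: Wald z error is then 8.3%, and the 10-df site-level test has 94% power for .12 vs .30. The proportion-scale reading is used here because it returns the plan's own figures.

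What remains is that, under the plan as written, analysts could choose tests with materially different error rates, and the stated power belongs to the liberal end of that choice.

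**Conclusion.** The point holds in a conditional form. The randomisation is by matched pair; the primary models omit the pairs and any small-sample method; and the stated power corresponds to a large-sample, unpaired test. Under Wald z, error at nominal 5% could range from about 10% down to about 3% as the shared variance goes from 0% to 75%; with uninformative matching, a likelihood-ratio test runs at 7–8%.

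With no matching gain, 10 df lowers the stated power by about 4 to 12 points (85% to 78–81%, 95% to 88%, 83% to 71%). A fully paired test lowers it by about 14 to 27 points (to 68–71%, 75% and 56%). At 50% shared variance the paired test exceeds 85% for .12 vs .30 but misses both interim figures; at 75% it meets all three.

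These sizes rest on ICC .05 on the proportion scale, 75 analysed per site (50 at the interim), two-sided tests and no covariates.

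**What to change.** Before any comparative analysis, including the interim:

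1. Name one small-sample primary test for both objectives. Examples are a site-level t-test on covariate-adjusted residuals, or a mixed model with small-sample degrees of freedom. Applying 10 df to a maximum-likelihood Wald statistic is not quite enough (6–7% in Step 3).
2. State in advance how the randomised pairs enter the analysis. Several choices are defensible; what matters is that the choice is not made after seeing the data.
3. Restate Table 4, with a row for SOC 18%, and the Objective 2 interim and final power for that test over a range of matching correlations. State the ICC scale and the sidedness.

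The cost is SAP wording and a rerun of the power calculations, with no new participants or procedures. The downside is less favourable stated power: by the 4 to 12 points above with 10 df, and by more with a fully paired 5-df test if the matching is weak.

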### **(b) Study Population**

The primary target population for the study is HIV-positive pregnant women.

**Inclusion criteria for HIV-positive pregnant women:** All HIV-positive women presenting for PMTCT services at study hospitals during pregnancy will be eligible for enrollment in the proposed study. Pregnant women under the age of 18 are eligible for inclusion in this study. Since Kenyan law allows pregnant women the same capacity to consent as an adult, young women under the age of 18 will be able to provide consent for themselves. Mentor mothers will take additional time with young women to ensure comprehension, emphasizing that participation is optional and not a requirement for receiving standard PMTCT/EID services for themselves or their infant.

Participants who do not own a mobile phone are also eligible for study enrollment. Investigators will not provide mobile phones to women but, rather, will evaluate the efficacy of the intervention's other components (alerts to provider for missed services) among participants without phones. Mobile phone ownership will be assessed as a mediator/moderator of intervention effectiveness.

**Exclusion criteria for HIV-positive pregnant women:** HIV-positive pregnant women will be excluded from study participation if she has any condition (including drug abuse, alcohol abuse, or psychiatric disorder) that study or hospital staff feel precludes her from providing informed consent. Capacity will be determined at the time of consent. Additionally, women who transfer care from one study site to another during their PMTCT services will be ineligible for enrollment at their new facility.

To assess mediators and moderators of HITSystem effectiveness, as well as part of the objective 4 evaluation of facility adoption, we will also interview providers at intervention and control hospitals.

**Inclusion criteria for providers:** Providers will be eligible to complete the survey if they (1) work primarily in ANC, PMTCT, CCC, laboratory, or MCH departments, (2) will have been involved in the provision of PMTCT care during the course of the study, and (3) have interacted with the HITSystem 2.1 during the course of the study (intervention sites, only).

**Exclusion criteria for providers:** Providers will be excluded from survey eligibility if they do not provide informed consent.

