**Participant surveys:** A brief enrollment survey will collect same demographic and clinical data at control sites (without HITSystem 2.1) in addition to patient-level data regarding PMTCT information, motivation, partner status and support, HIV disclosure, depression (modified Edinburgh postnatal scale), and risk of violence (both arms, Appendix 2A). Repeated surveys after delivery and 6m postpartum (for VL sample collection described in Objective 2, both arms) will include these same patient-level measures to assess any changes that may mediate or moderate intervention impact (Appendices 2B & 2C). Participants will be compensated 200 KES for completion of each survey.

**Facility assessment form** (Appendix 2D) will be completed at the beginning, mid-point and end of study implementation to assess average resource level, annual PMTCT volume, and PMTCT provider-patient ratios.

**Provider surveys:** At baseline and again at the end of the study period, providers in both arms will be asked to complete a short survey (Appendix 2E) assessing provider role/ department, level of experience, knowledge and motivation regarding current PMTCT guidelines, and barriers and facilitators to provision of complete PMTCT services. We estimate n=5 providers per site to complete the survey for a total of n=60 providers (n=30 intervention, n=30 control). Prior to completing the survey, providers will complete an informed consent (Appendix 2C). Providers will be compensated 500 KES for completion of each survey.

**Supportive Supervision Visits** will occur monthly at all sites. During these visits, Site Coordinators will provide technical assistance and retraining, review study materials (informed consent forms, surveys), and review data for completeness and accuracy. The monthly frequency of site visits approximates programmatic HITSystem 1.0 implementation support in Kenya.

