### PMTCT Knowledge

Please choose the best answer:

32. During pregnancy, I should receive viral load testing:
- Never, viral load testing is only conducted after delivery
  - Between 1 and 2 times.
  - At least three times.
  - Don't know
33. During pregnancy, it is recommended that HIV+ women take ART medications only if they are feeling unwell.....True / False
34. It is recommended that I attend a minimum of how many ANC appointments?
- 2
  - 3
  - 4
  - 5

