### PMTCT Knowledge

19. With what frequency should HIV+ mothers with undetectable viral loads receive a viral load test while they are breastfeeding their baby?
- Every 3 months
  - Every 6 months
  - Every 12 months
  - Only after their infant has stopped breastfeeding
20. When should HIV+ mothers stop taking their ART?
- Not until the infant begins eating solid food, at around 6 months.
  - Not until the infant stops breastfeeding.
  - Not until the infant has been confirmed HIV-negative at 18 months of age
  - Never, the mother should continue lifelong ART for her own health.
21. It is recommended that babies continue being routinely tested for HIV until when:
- 6 months of age
  - 12 months of age
  - 18 months of age
  - 2 years of age
  - The baby stops breastfeeding

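### The knowledge and motivation models name neither site nor study arm, which overstates the evidence for site-average provider scores, and enrolment questions do not match the follow-up surveys

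*Combined protocol and SAP*

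**What the plan says.** **Model.** Under Statistical analyses for objective 1, the primary test of completion is fitted "using logistic mixed models with a random site intercept (to adjust for clustering"). For the mediation step, "we will compute average levels of provider knowledge and motivation for each site at baseline and end of study". The scores are to be compared before and after the intervention and between arms. Then "provider and patient knowledge and motivation will be examined as predictors of PMTCT completion using logistic regression". That sentence mentions no site effect, clustering adjustment or arm term. The Objective 1 outcomes text confirms that provider characteristics are handled at facility level. Under Statistical analyses for Objective 2, "The same methods described for mediation analysis of information and motivation will be applied in Objective 2".

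**Patient surveys.** Under Participant surveys, the delivery and 6-month rounds "will include these same patient-level measures to assess any changes that may mediate or moderate intervention impact", where the measures meant are those of the enrolment survey.

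**Provider eligibility.** Section 5.0(b) sets three criteria. The third is that providers must "have interacted with the HITSystem 2.1 during the course of the study (intervention sites, only"). Providers are surveyed at baseline and at the end of the study.

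**The concern.** All women at a site share the same provider score. A logistic regression that treats women as independent counts about 900 observations for a predictor that has 12. Chance differences between sites can then pass as evidence that provider knowledge or motivation drives completion. The plan intends these analyses to show how HITSystem 2.1 works, so a spurious provider pathway could steer later implementation.

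The patient scores raise a different problem. If the questions change between enrolment and follow-up, a before-after difference mixes real change with the change of instrument.

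The third provider criterion cannot be met at a survey taken before the system is in use. At study end it limits intervention-site respondents to users, and control sites have no matching restriction.

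**Working it through.** **Inputs.** From Sample size determination for Objective 1: ICC .05, six clusters per arm, 75 women per cluster, 85% power. From Table 4: the four pairs of completion rates. Two-sided 5% tests are assumed. The scale of the ICC is not stated, so both the proportion scale and the logit scale are shown.

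**1. Reproducing the plan's figure.** Design effect = 1 + (75 − 1) × .05 = 4.7. Effective n per arm = 450 / 4.7 = 95.7. Power = Φ[(Δ − 1.96·SE₀)/SE₁]. For .12 v .30:
- SE₀ = √(2 × .21 × .79 / 95.7) = .0589
- SE₁ = √((.12 × .88 + .30 × .70) / 95.7) = .0574
- power = .87

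The four Table 4 rows give .861, .863, .870 and .847, so the stated 85% is recovered within about 2 points. The plan's own power calculation therefore uses the clustering that the mediation sentence leaves out.

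**2. Closed form for a site-level predictor.** The standard error is understated by √4.7 = 2.17. The true rejection rate of a nominal 5% test is 2 × [1 − Φ(1.96 / √DE)]:
- ICC .01: DE 1.74, rate 13.7%
- ICC .05: DE 4.7, rate 36.6%
- ICC .10: DE 8.4, rate 49.9%

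**3. Simulation.** There were 12 sites of 75 women, completion .12 v .30, a provider score with no effect, and 4,000 trials per case. The comparison method regresses site empirical logits on score and arm, with t inference on 12 − 3 = 9 df.

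| ICC | Logistic, arm included: proportion scale | Same: logit scale | Site-level, 9 df |
|---|---|---|---|
| .01 | 13.7% | 10.2% | 4.9–5.0% |
| .02 | 22.1% | 15.0% | 4.3–4.9% |
| .05 | 35.6% | 27.2% | 5.2–5.4% |
| .10 | 49.6% | 40.1% | 4.7–5.0% |

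At ICC .05 (proportion scale), leaving arm out raises the logistic rate to 51.6%. Suppose the intervention also moves the score by 1 SD (an assumption) with no path to the outcome. With arm omitted the rate is then 70.1%, and 16.7% even with site-level inference. The arm term is therefore needed as well as the site term.

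**4. Patient-level scores.** For a binary patient score with no effect (outcome ICC .05, arm included, 3,000 trials), the rejection rate is 5.1%, 5.9%, 7.1% and 8.9% when the score's own ICC is 0, .02, .05 and .10. Those score ICCs are assumptions.

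**5. The survey forms side by side (English).**
- *Knowledge.* Enrolment items 32–34 cover testing in pregnancy ("During pregnancy, I should receive viral load testing"), when to take ART and the number of antenatal visits. Delivery items 25–27 cover prevention methods and infant testing. The 6-month items 19–21 start with "With what frequency should HIV+ mothers with undetectable viral loads receive a viral load test" while breastfeeding, then ask about stopping ART and the end of infant testing. Enrolment shares no item with either later form. Delivery 27 and 6-month 21 are the same.
- *Motivation.* Of enrolment items 35–39, three (adherence, competing commitments, attending appointments) return reworded for the infant period. Two (facility delivery, transport) do not return. Delivery 28–33 and 6-month 22–27 are the same six items.
- *Partner support.* Enrolment 21–22 ask about importance and expectation. Delivery 12 and 6-month 9 ask how often support was given. Items b, d, f, g and h match between those two forms, although the top response is labelled differently.
- The depression and violence items are essentially unchanged throughout, so the claim of sameness holds for those.

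**The case against.** The strongest reply is that logistic regression may be shorthand. The same paragraph names the mixed model, and Objective 2 again specifies adjustment for clustering. That reading is plausible. However, the plan states the adjustment for one analysis and omits it for the next, so an analyst could follow the text either way.

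A reader might infer that the plan is bound to report false mediators. The documents do not support that. The risk is raised mainly for provider scores, its size depends on the ICC and its scale, and patient scores are little affected.

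A reader might also infer that the differing questions bias the comparison of arms. They do not by themselves, because both arms answer the same form at each visit and the plan compares arms as well as time points. On partner support, the Objective 1 text may mean change between delivery and 6 months only, and for that several items match. What stands is that change from enrolment is not interpretable.

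On providers, it is tempting to say that control providers are unrestricted and that intervention scores are inflated. The first two criteria (department, involvement in care) bind both arms, and nothing in the documents gives a size or direction for any bias. Appendix IIE limits its HITSystem questions to intervention sites at study end, so the form itself does not presuppose use at baseline. The eligibility wording still does.

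Finally, correct inference does not turn this into a mediation analysis, because the plan defines no indirect effect. That is fair, and it is a reason to label the results exploratory.

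**Conclusion.** The point holds in two main parts and one lesser part.

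**Provider scores.** Followed as written, with women treated as independent, the regression would call a null site-average score significant in about 27–37% of trials at the plan's ICC of .05 with arm included. The figure is 10–14% at ICC .01, 40–50% at ICC .10, and about 52% at ICC .05 with arm omitted (proportion scale). These figures assume 75 analysed women per site and completion of .12 v .30. For patient scores the rate is about 5–9%.

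**Change from enrolment.** Change in patient knowledge, motivation and partner support cannot be interpreted, because the enrolment questions differ. This spoils within-arm change and does not create a between-arm difference.

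**Provider criterion.** The third criterion is unworkable at baseline and selects users in one arm at study end. Its effect is unquantified.

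Neither primary comparison is affected.

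**What to change.** 1. **Models (both objectives).** State that every predictor and mediator model of knowledge and motivation includes the random site intercept and study arm, that site-level provider scores are tested on site-level degrees of freedom (about 9), and that the results are exploratory. Existing data suffice. The price is wide intervals: at 9 df the critical t is 2.262, so p < .05 needs a partial correlation of 2.262 / √(2.262² + 9) ≈ .60.

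2. **Patient scores.** For knowledge, motivation and partner support, replace change from enrolment with a between-arm comparison at delivery and at 6 months, using the enrolment score as a covariate. Compute change only for items common to those two visits: the six motivation items, the knowledge item on when infant testing ends, and the matching partner-support items. Check the translations first. The Luo 6-month version of the motivation item on competing commitments appears to refer to six months where the delivery version refers to six weeks. No new data are needed.

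3. **Provider survey (secondary).** Do not apply the third criterion to the baseline survey or to the between-arm provider comparison. Record system use as a variable instead. Appendix IIE already asks about use, but its days-per-week item starts at one day and needs a zero option. Some non-users would have to be surveyed at study end, and a fresh baseline round is probably no longer feasible because two sites have already closed enrolment.
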